8.3 EXCLUSION CRITERIA

If a patient meets any of the following criteria, he or she is *not* eligible:

1. Patients with a history of congestive heart failure of Class 2 or higher as graded using the New York Heart Association scale (scale provided in [Appendix 5](#))
2. Patients with a history of angina pectoris grade 2 or higher as graded using the Canadian Cardiovascular Society grading scale (scale provided in [Appendix 5](#))
3. History of ventricular tachycardia, torsade de pointes, family history of sudden death, myocardial infarction or acute coronary syndrome within the previous 3 months, as reported by the patient.
4. Serum potassium below the laboratory lower limit of normality at the TR03 Visit 5. Note: Potassium levels below the laboratory lower limit of normal at Visit 6/Visit 1a should be repeated and potassium supplementation provided as appropriate.
5. QTcF interval >450ms on screening/Visit 1a ECG
6. Heart rate <50 BPM on any screening assessment. Patients with a resting heart rate of <50 bpm will have it repeated once after 5 minutes in the supine position, and if it remains <50 bpm during the repeat, they will be considered a screen failure
7. Use of a medication known to be associated with risk of torsade de pointes (see [Section 9.7.8](#), Safety Assessments, for hyperlink to the CredibleMeds Filtered QTDrug List for cardiovascular related prohibited medications with a known associated risk of Torsade de Pointes)
8. History of substance abuse within the past year as determined by the Investigator
9. Significant medical condition or other factors that in the opinion of the Investigator may interfere with the conduct of the study
10. Known hypersensitivity or allergy to nalbuphine or formulation components
11. Is a pregnant or lactating female.

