Patients can enroll into TR03ext and receive drug as early as approximately 2 weeks following their last dose of study drug in the parent study TR03. Approximately one-third of patients are expected to enter the study after having received placebo in TR03. These patients are expected to have a high level of pruritus intensity. On the other hand, some patients who have received active treatment in TR03 may still have either reverted to their original pruritic conditions or may have a residual anti-pruritic effects from the drug treatment even following the 2-week wash out period. To allow for various starting levels of pruritus intensity, patients who have Worst Itch NRS that is ≥ 5 will enter the Treatment Period upon completion of Visit 1a. Patients whose Worst Itch NRS score is < 5 will be entered into an extended screening period, no-treatment criteria Observation Period for up to 12 weeks or until they develop a higher level of pruritus (i.e., Worst Itch NRS ≥ 5), at which point they will transition to the Treatment Period upon completion of Visit 1b. All patients entering the Treatment Period, whether immediately upon study entry or following a period of time in the Observation Period, will initially be titrated to a dose that can be as high as 180 mg BID during the first 4 weeks of the Treatment Period (See [Table 3](#) for dosing schedule). Patients who continue in the Observation Period and maintain a Worst Itch NRS score of < 5 will be screen failed from the study at the end of the 12-week period. While patients remain in the Observation Period, they will not be considered as enrolled into the study, but as participating in an extended screening process until they are eligible for treatment.

Patients, who fail to improve, as defined by the failure-to-improve criteria, will be taken off study drug treatment. A failure-to-improve criteria is implemented beginning on TV 3 and at every subsequent Treatment Visit, and is described in [Section 11.1](#). The rationale for the failure-to-improve criteria is based on the following: Following a maximal titration period of up to 3-weeks, an approximate 2-week window on stable drug dose should be sufficient for the drug to start eliciting a beneficial effect. The patient's self-reporting of pruritus intensity at each visit, beginning at TV 3, will be compared to the baseline value of the

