9.6 STUDY PROCEDURES

Before the initiation of study-specific procedures the patient must be given a complete explanation of the purpose of the study, evaluations to be conducted, and risks/benefits for study participation. Patients must understand the requirements of the study, provide informed consent (See [Section 9.6.1](#) and [Section 20.3](#)), agree to the study restrictions, and agree to return for the required assessments. After review of the informed consent is documented, the patient must give written consent. For this study, patients will retain their study number from study TR03.

With the exception of Visits 1a and 1b, windows for all visits will be +/-3 Days. Please see the Schedule of Events in [Appendix 1](#) for details of the Titration Period assessments and the Study Schematics Flow Charts in [Appendix 2](#). See [Section 9.7.1](#) for details of Study Drug Dosing and [Section 9.7.6.4](#) for information on the use of pre-medications with the Study Drug. Visit 6 of TR03 will serve as TR03ext Visit 1a unless these visits do not occur on the same calendar day.

Visit 1a has procedures to be done as summarized in [Section 9.6.1](#) regardless of the patient's pruritus intensity score. Following a set of common procedures, only patients who qualify for the Treatment Period based on meeting the pruritus intensity criteria will be eligible to receive study drug; Visit 1a corresponds to TV1. For patients who, during the final visit of TR03, did not meet the pruritus intensity criteria to enter the TR03ext Treatment Period, Visit 1a corresponds to OV1, the first visit of the Observation Period. If during a subsequent observation period visit to the site, the patient meets the pruritus intensity criteria, then that observation visit immediately transitions into Visit 1b (it also corresponds to TV1 since it is now the first Treatment Period visit) – See [Section 9.6.3.3](#) and [Section 9.6.4](#).

For patients who transition to the Treatment Period from the Observation Period, [Table 8](#) provides details on the treatment visit schedule based on the study week that the patient transitioned from the Observation Period to the Treatment Period. The patient will follow the Treatment Visit schedule outlined on the Schedule of Events ([Appendix 1](#)).

For clarity,

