Patients with a Worst Itch NRS greater than 5 (≥ 5) enter the Treatment Period and will receive Study Drug starting with an evening 30 mg dose (to be taken at home), after the Visit 1a (or Visit 1b) procedures have been completed.

Receipt of the first dose of study drug will define Day 1. Visit 1a or Visit 1b for these patients is also Treatment Visit 1 (TV1). Subsequent visits will be defined as TV2, TV3, etc.

Patients with a Worst Itch NRS less than 5 (<5) enter the Observation Period and will not receive study drug treatment. Visit 1a for these patients is also Observational Visit 1 (OV1). Subsequent visits will be defined as OV2, OV3, etc.

Patients in the observation period can be followed for up to 12 weeks.

If during the Observation Period, a patient's Worst Itch NRS increases to greater than or equal to 5 (≥ 5) and the patient meets all other eligibility criteria, Visit 1b procedures are to be performed. The patient's next visit will be Treatment Visit 2 (TV2). Do not repeat the Worst Itch NRS during Visit 1b.

If, however, at Observation Visit 12 the patient does not have a Worst Itch NRS greater than or equal to 5 (≥ 5), the patient will be screen failed without having initiated treatment with nalbuphine.

[Figure 2](#), [Figure 3](#) and [Figure 4](#) visually display the relationship between TR03ext study weeks, Treatment Period weeks and Observation Period weeks.

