9.6.2.1.2 TV 2 (Treatment Week 3)

The following procedures are to take place at this visit:

- complete PAS
- obtain vital signs
- collect urine for pregnancy test (regardless of sexual activity and confirm negative status prior to dispensing additional study drug)
- collect blood for PK
- perform 12-Lead ECG after at least 5 minutes in a supine position (See the Study Reference Manual for ECG procedures, [Section 17.4](#) Electrocardiograms for the handling of Cardiovascular adverse events)
- perform brief neurological assessment
- administer PRO measurements (paper versions):
 - Worst itch NRS
 - Average itch intensity NRS
 - VRS
 - ItchyQoL
 - MOS Sleep-R
 - HADS.

The PRO questionnaires must be administered at the study site under the supervision of and by trained study staff, strictly adhering to PRO Administration Instructions (see Study Reference Manual).

- record AEs (including tolerability to study drug)
- review concomitant medications, including over-the-counter medications, nutritional supplements, and vitamins
- reinforce and document patient's compliance with dosing and all other required study related procedures (i.e. rescue medication log, dosing diary, etc.)
- perform Study Drug accountability, retrieve previously dispensed Study Drug
- dispense enough Study Drug to the patient for required dosing until their return at TV3 (Treatment Week 5)
- document tolerability/intolerability to study drug and titration decision based on [Table 3](#)
- discontinue study medication in patients who do not tolerate 30 mg BID dose and complete the End of Treatment Visit, TV14 (See [Section 9.6.2.2.12](#) and [Section 11](#))

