 - VRS
 - ItchyQoL
 - MOS Sleep-R
 - HADS
 - record AEs
 - record concomitant medications
 - If the Worst Itch NRS is greater than or equal to 5 (≥ 5), transition the patient to the Treatment Period and conduct Visit 1b procedures (described in [Section 9.6.4](#)) on the same day as this visit. See [Table 8](#) for a summary related to future Treatment Period Visits.

Patients whose Worst Itch NRS is less than 5 (<5) at the OV4 should be screen failed from the study. No Washout/Safety follow-up visit is to take place.

9.6.3.3 *Transitioning from the Observation Period to the Treatment Period*

- For patients who have a Worst NRS score that is greater than or equal to 5 (≥ 5) at Observation Visit 2, 3, or 4, complete Visit 1b procedures (see [Section 9.6.4](#)).
- These patients will receive up to 46 weeks of study medication treatment.
- See [Table 8](#) for the Treatment Period Visits to be completed post Visit 1b, as well as the number of weeks of study drug to dispense at each Treatment Visit and when to schedule the End of Treatment Visit 14 (TV14) to take place.
- See [Section 9.6.2](#) and the Schedule of Events ([Appendix 1](#)) for procedures to be performed at each applicable Treatment Visit.

9.6.4 **Transition to Treatment Period (Visit 1b)**

Confirm each patient's eligibility (see [Sections 8.2](#) and [8.3](#)) prior to performing any Visit 1b procedures. If the patient does not meet eligibility requirements, do not perform any Visit 1b procedures; the patient is to be screen failed.

See [Table 4](#) for summary of Visit 1b procedures.

Patients evaluated at OV 2-4 who record a Worst itch NRS greater than or equal to 5 (≥ 5) and, are otherwise eligible, can immediately begin Visit 1b and transition into the Treatment Period. The following procedures are to take place at this visit:

- obtain vital signs
- conduct a physical examination
- collect central laboratory samples (hematology and chemistry)
- collect serum pregnancy test sample in women of childbearing potential (regardless of sexual activity) and send for processing at the central laboratory*
- collect urine for central lab urinalysis
- urine for pregnancy test (regardless of sexual activity) and confirm negative status prior to dispensing study drug*

* If the urine pregnancy test result is negative and the serum pregnancy test result is positive, the patient is to be contacted and the following actions are to take place:

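### For patients entering treatment from the Observation Period, the 450 ms QTcF entry limit is checked on a Visit 1a ECG about 4, 8 or 12 weeks old, and no QTcF limit is applied to the pre-dose Visit 1b ECG

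*Protocol*

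**What the plan says.** Exclusion 5 (Section 8.3 and the synopsis) is "QTcF interval >450ms on screening/Visit 1a ECG". Exclusion 6 is worded more broadly: "Heart rate <50 BPM on any screening assessment", with a repeat measurement, and "if it remains <50 bpm during the repeat, they will be considered a screen failure".

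Patients with a Worst Itch NRS below 5 at Visit 1a go into the Observation Period. Section 9.2 says that "they will not be considered as enrolled into the study, but as participating in an extended screening process until they are eligible for treatment". Once the score reaches 5 or more, Section 9.6 says "that observation visit immediately transitions into Visit 1b", and that if "the patient meets all other eligibility criteria, Visit 1b procedures are to be performed".

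Section 9.6.4 sets the order. Eligibility under Sections 8.2 and 8.3 is confirmed "prior to performing any Visit 1b procedures. If the patient does not meet eligibility requirements, do not perform any Visit 1b procedures". Vital signs, laboratory samples, the 12-lead ECG, dispensing and instructions for a first dose at home that evening all follow as Visit 1b procedures.

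Table 4 ticks Confirm Eligibility at Visit 1a only, and its footnote 4 makes Visit 1b the first visit of the Treatment Period. Table 7 lists no ECG at OV2, OV3 or OV4. Section 17.4 assigns the local ECG reading to clinical significance and the interval measurements, including QTcF, to the central reading. Its stop rule needs a QTcF above 500 ms together with a rise above 60 ms from baseline.

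**The concern.** The protocol sets a QTcF entry limit and schedules a pre-treatment ECG at Visit 1b, but does not connect the two. The eligibility check comes before the ECG, so the ECG cannot inform it. The only study ECG then available for exclusion 5 is the one from Visit 1a, taken one to three months earlier.

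At stake is a cardiac safety criterion in a study whose primary objective is safety and tolerability. A patient whose QTcF rose above 450 ms during the Observation Period could meet the eligibility check on the old ECG and take the first dose that evening, with no stated limit applied to the new one. Two sites could also handle the same Visit 1b value differently, because the text leaves them to decide whether exclusion 5 reaches it.

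**Working it through.** No sample size, power or error rate is involved. The check sets the provisions side by side and adds date and threshold arithmetic.

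**Which ECG the check can use**

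1. Section 9.6.1 takes a 12-lead ECG at Visit 1a from every patient, including those who go on to observation.
2. Sections 9.6.3.1 and 9.6.3.2 and Table 7 take none at OV2 to OV4.
3. Section 9.6.4 confirms eligibility first and performs the Visit 1b ECG afterwards.
4. The study ECG available at the check is therefore the Visit 1a ECG, which is also the one that exclusion 5 names.

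**How old that ECG is**

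Take Visit 1a as day 0, and OV2, OV3 and OV4 at weeks 4, 8 and 12 with the ±3 day window of Table 7. Age = 7 × week ± 3.

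| Transition at | Nominal age | Range |
|---|---|---|
| OV2 | 7 × 4 = 28 days | 25-31 days |
| OV3 | 7 × 8 = 56 days | 53-59 days |
| OV4 | 7 × 12 = 84 days | 81-87 days |

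Table 8 agrees. It allows 46, 42 and 38 weeks of treatment out of 50, which leaves 4, 8 and 12 weeks of observation.

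**Whether Section 17.4 closes the gap**

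The rule requires QTcF > 500 ms and QTcF − baseline > 60 ms. The protocol does not define the ECG baseline, so both candidates are tried.

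- *Visit 1a as baseline* (450 ms or less, since the patient was eligible). A Visit 1b value of 451-500 ms is not above 500 ms, so the first condition fails. For a Visit 1a value of 450 ms, the rule needs more than 450 + 60 = 510 ms.
- *Visit 1b as baseline*. The rise at Visit 1b is 0 ms, so the second condition fails at any value.

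A value of 451-500 ms therefore cannot meet the rule under either baseline. Where the rule does apply, it leads to a repeat ECG, core-laboratory confirmation and discontinuation. It is not written as a hold on the first dose.

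**Other provisions**

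- Section 10.1 supplies drug after eligibility is confirmed, which Section 9.6.4 places before the ECG.
- Section 9.7.8 and Appendix 5 provide angina and heart-failure grading and a list of prohibited drugs. None contains a QTcF cut-off.
- Exclusion 9, Section 12 and the local ECG reading allow judgment but set no number.
- By contrast, the urine pregnancy test in Section 9.6.4 must be negative before drug is dispensed. A Visit 1b result can therefore gate dispensing where the protocol says so. The ECG has no equivalent step.

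**The case against.** The strongest reply is that Visit 1b still belongs to screening. Observation patients are not yet enrolled, Table 4 footnote 10 makes the first dose the point of enrollment, and Section 19.9.6 treats the Visit 1a/1b ECG as pre-treatment. On that view the word screening in exclusion 5 already covers the Visit 1b ECG. The pregnancy tests also show that the opening check in Section 9.6.4 is not final for every criterion. This makes the intent arguable. It does not remove the problem, because the reading conflicts with the order in Section 9.6.4 and with Table 4, and only pregnancy has an explicit later gate. If it is the intended reading, those two places need correcting.

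A second reply is that anchoring a criterion to an earlier visit may be deliberate, since exclusion 4 uses potassium from TR03 Visit 5. That is possible, but no reason is given for leaving the later pre-treatment ECG without a limit.

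Four stronger readings are tempting and are not supported:

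- *Nothing would act on a prolonged Visit 1b QTcF.* Sections 17.4 and 9.7.8 call for the Appendix 5 assessments if cardiovascular exclusion criteria arise, and the investigator may act on judgment. What is missing is a QTcF cut-off.
- *A direct entrant with the same value would reliably be stopped before dosing.* QTcF is read centrally, no turnaround or same-day site reading is stated, and direct entrants also dose on the evening of Visit 1a. The Study Reference Manual, which holds the ECG procedures, is not available here.
- *The dose reached before the next scheduled ECG, at Treatment Visit 2, measures the harm.* Direct entrants follow the same titration and ECG schedule.
- *The heart-rate limit is also bypassed.* Exclusion 6 covers any screening assessment and can be read to include the Visit 1b value. It is ambiguous, not absent.

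**Conclusion.** The point holds as an ordering and wording defect in the protocol. For Observation Period entrants, the QTcF limit is applied as written to an ECG about 4, 8 or 12 weeks old, and no QTcF limit is attached to the pre-treatment Visit 1b ECG. Followed literally, a patient with a pre-dose QTcF of 451-500 ms can start drug that evening unless someone intervenes on judgment.

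The practical effect is probably small. These patients are off study drug between the two visits, Section 3.3.2 reports no clinically relevant ECG findings in TR01, and Section 9.6.4 has the history and medication exclusions re-checked at Visit 1b. The protocol does not say how many patients will enter from observation or how often QTcF will cross 450 ms. The only bound is the study maximum of about 60 patients.

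The day counts assume that Visit 1a is day 0 and the observation weeks are nominal. The result for 451-500 ms does not depend on which visit is taken as the ECG baseline. The change should be made because it is cheap and concerns a stated safety limit. It does not call the study's design into question.

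**What to change.** - **Section 9.6.4:** keep the opening check for history and medication criteria, and add a second confirmation of eligibility after the Visit 1b vital signs and ECG and before dispensing.
- **Exclusion 5 (Section 8.3 and synopsis):** name the screening/Visit 1a ECG or the pre-dose Visit 1b ECG.
- **Exclusion 6:** say that the pre-dose Visit 1b heart rate counts.
- **Table 4:** tick Confirm Eligibility at Visit 1b.
- **Deciding reading:** state whether a same-day site QTcF decides, or the core-laboratory value with the first dose held until it is returned. Apply the same rule at Visit 1a.
- **Repeat ECGs:** if a repeat is allowed for a borderline QTcF, exempt it from the Section 19.9.6 requirement for prior written Sponsor approval.

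No extra ECG is needed. The cost is text edits, a decision on which reading governs, and an occasional screen failure or delayed first dose. If the core-laboratory value decides, its turnaround sets the length of the delay, and the protocol does not give that figure.

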9.6.5 Washout and Safety Follow-Up Period

All patients who received Treatment, but did not withdraw consent, will have a 2-week Washout and Safety Follow-Up Period following TV14. During this visit, the PRO questionnaires (paper versions) must be administered at the study site under the supervision of and by trained study staff, strictly adhering to PRO Administration Instructions (see Study Reference Manual). Please see the Schedule of Events in [Appendix 1](#) for details of the Washout and Safety Follow-Up Period assessments. Additional information for this visit is provided below.

For patients who entered the Treatment Period at Visit 1a, the Washout and Safety Follow-Up Period Visit would take place during week 53, post TV14. However, for a patient who enters the Treatment Period at Visit 1b, the Washout and Safety Follow-up Period Visit will take place 14 days (plus the visit window) post TV14.

For patients who met Failure-to-Improve criteria or who discontinue treatment for other reasons (see [Section 11.1](#)), this visit is to take place 14 days (+ 7 days) after TV14.

The following procedures are to take place at this visit:

- obtain vital signs
- perform 12-Lead ECG after at least 5 minutes in a supine position (See the Study Reference Manual for ECG procedures, [Section 17.4](#) Electrocardiograms for the handling of Cardiovascular adverse events)
- perform brief neurological assessment
- collect blood for central laboratory measurements and PK
- administer PRO measurements (paper versions):
 - Worst itch NRS
 - Average itch intensity NRS
 - VRS
 - ItchyQoL
 - MOS Sleep-R
 - HADS

The PRO questionnaires must be administered at the study site under the supervision of and by trained study staff, strictly adhering to PRO Administration Instructions (see Study Reference Manual).

- AEs and concomitant medications (including rescue medications) will be recorded
- collect the Rescue Medication Log from the patient at this visit
- retrieve any remaining study drug not previously returned by the patient
- retrieve the 14 day SOWS packet

For patients who prematurely discontinued study medication for reasons other than withdrawal of consent, schedule the Premature Discontinuation of Study Drug Follow-up Telephone Contact visit.

9.6.6 Premature Discontinuation of Study Drug Follow-up Telephone Contact Visit

Patients who prematurely discontinued study drug during the study, for reasons other than withdrawal of consent, will have completed TV14 and the Washout and Follow-up Safety

Period Visit. These patients are to be contacted by telephone 30 days (+ 2 weeks) after the visit that the patient met the Failure-to-Improve criteria and stopped study drug.

During this Telephone Contact, record AEs and changes in concomitant medications since the completion of the Washout and Follow-up Safety Period Visit.

Document any additional efforts that take place to reach a patient who is non-responsive to telephone contact.

